1.3.3.1 Electrocardiographic experience with RUXOLITINIB

A thorough QT study [INC18424-138] was performed to assess the heart rate corrected QT interval in healthy subjects dosed with a single dose of 25 mg and 200 mg of RUXOLITINIB, compared to placebo and moxifloxacin. The pharmacokinetic parameters observed in this study were consistent with those reported from previous clinical studies conducted in healthy volunteers. Based on the ICH E14 this study met the requirements for a negative QT study. For RUXOLITINIB dosing, at no time did the upper bound of the 2-sided 90% confidence interval exceed 10 msec. The largest mean change was seen following the 200 mg dose, which was 3.7 beats per minute at 1.5 hours post-dose. This was not considered clinically significant by the expert cardiologist at the central ECG laboratory. There was also no evidence that increasing plasma concentrations of RUXOLITINIB was associated with increases in the change of QTc.

1.3.4 RUXOLITINIB clinical pharmacokinetics

In clinical studies, RUXOLITINIB is completely and rapidly absorbed after oral administration with maximal plasma concentration (C_{max}) achieved approximately 1.5 hours post-dose. Administration with a high-fat meal decreased RUXOLITINIB mean C_{max} by 24% and increased RUXOLITINIB mean AUC by 4%. A linear dose-exposure relationship was observed over a dose range of 5 to 200 mg (single dose). There was minimal accumulation (12%) with multiple dose administration (q12h x 10 days) compared single dose administration. The steady state dose-exposure was linear over the dose range of 15 to 50 mg q12hours. In vitro studies indicate that CYP3A4 is the major enzyme responsible for metabolism of RUXOLITINIB. At clinically relevant concentrations, RUXOLITINIB is not expected to inhibit CYP1A2, CYP2B6, CYP2C8, CYP2C9, CYP2C19, CYP2D6 or CYP3A4 and is not a potent inducer of CYP1A2, CYP2B6 or CYP3A4. RUXOLITINIB is eliminated almost completely by oxidative metabolism with a terminal elimination half-life of approximately 3 h. Following a single oral dose of [^{14}C]-labeled RUXOLITINIB in healthy adult volunteers, 74% of radioactivity excreted in urine and 22% excretion via feces. Unchanged RUXOLITINIB accounted for less than 1% of the excreted total radioactivity.

The pharmacodynamic activity of RUXOLITINIB was characterized by an ex vivo whole blood assay that involves quantitation of pSTAT3 following IL-6 stimulation. Following oral, single or multiple dose administration in healthy subjects, RUXOLITINIB demonstrated dose dependent inhibition of ex vivo cytokine-induced pSTAT3 with maximal inhibition occurring at 1-2 hours after administration for all doses, coincident with maximal RUXOLITINIB levels. The oxidative metabolites of RUXOLITINIB retain pharmacologic activity to varying degrees albeit with 2-5-fold greater IC_{50} compared to the parent compound and represent approximately 20% of overall activity (inhibition of IL-6 stimulated STAT3 phosphorylation in whole blood) observed after a RUXOLITINIB dose.

In vitro metabolism studies strongly suggest that CYP3A4 is the predominant human CYP isozyme responsible for the metabolism of RUXOLITINIB. Co-administration of RUXOLITINIB with ketoconazole, a potent CYP3A4 inhibitor, resulted in an approximate doubling of plasma AUC, whereas co-administration with erythromycin, a moderate CYP3A4 inhibitor, caused approximately 27% increase in exposure. In the presence of rifampin, a potent inducer of CYP3A4, an approximate 70% decrease in plasma AUC of RUXOLITINIB was observed.

In patients with varying degrees of renal impairment, the pharmacokinetics and pharmacodynamics of RUXOLITINIB was similar to the healthy subjects, except in patients with end stage renal disease on hemodialysis who exhibited modestly higher response in the pSTAT3 assay when dosed following dialysis. The recovery of RUXOLITINIB in dialysate was negligible, consistent with the high serum protein binding (97%) of RUXOLITINIB. There was little effect on the plasma C_{max} values of RUXOLITINIB metabolites, whereas the AUC values of RUXOLITINIB metabolites tended to increase with increasing severity of renal impairment, and most markedly in the subjects with end stage renal disease requiring hemodialysis. The metabolites appeared to be dialyzable to varying degrees in a 4-hour hemodialysis procedure.

In patients with hepatic impairment there was no rank order correlation between exposure and degree of hepatic impairment assessed by Child-Pugh scores. RUXOLITINIB AUC increased 88% in mild, 29% in moderate, and 66% in severe disease. The terminal elimination half-life ranged from 4.6 hours in mild, 4.1 hours in moderate and 5.1 hours in severe hepatic impairment compared to 2.8 hours in healthy subjects. No significant differences in pharmacodynamics were observed among subjects with mild or moderate hepatic impairment compared to healthy subjects. In subjects with severe hepatic impairment, the inhibition of IL-6 stimulated pSTAT3 levels appeared to be prolonged. Hepatic impairment, in general, decreased the plasma C_{max} but not the AUC values of RUXOLITINIB metabolites, and no correlation was observed between the change in pharmacokinetic parameters of the metabolites and the degree of hepatic impairment.

Additional details as to the clinical pharmacology of RUXOLITINIB may be found in the IB.

1.4 Risk assessment of the combination of PANOBINOSTAT and RUXOLITINIB

1.4.1 Assessment of drug-interaction potential between PANOBINOSTAT and RUXOLITINIB

Based on *in vitro* metabolic profiling and results from clinical PANOBINOSTAT drug interaction studies ([CLBH589B2110] and [CLBH589B2109]), PANOBINOSTAT was shown to be a non-sensitive CYP3A substrate and a weak CYP2D6 inhibitor in patients. It has also been predicted to have minimal clinical drug interaction risk with a non-sensitive CYP3A substrate.

RUXOLITINIB was also shown to be a non-sensitive CYP3A substrate based on the results from Study [INCB18424-133] (ketoconazole inhibition study) and is not known to be a CYP inhibitor or inducer *in vitro*.

Since CYP3A is the most abundant CYP enzyme in the liver, drugs with shared elimination pathway via CYP3A had not been shown to have compromised elimination. Drug-interaction between PANOBINOSTAT and RUXOLITINIB is therefore not expected by being CYP3A substrates. Based on available *in vitro* and clinical data, clinical drug interaction between PANOBINOSTAT and RUXOLITINIB is therefore not expected.

PANOBINOSTAT is a weak time-dependent CYP3A inhibitor and predicted to have no clinically relevant consequence on a non-sensitive CYP3A substrate, such as RUXOLITINIB. As PANOBINOSTAT is also administered intermittently, its clinical impact on the chronic RUXOLITINIB administration is deemed even more remote.

1.4.2 Integrative toxicological assessment of PANOBINOSTAT and RUXOLITINIB in combination

When combining both compounds the potential for overlapping toxicities needs to be considered. For PANOBINOSTAT the predominant toxicities seen preclinically consisted of: myelosuppression, lymphoid depletion, degeneration of the intestinal epithelium, variable effects on the thyroid epithelium and thyroid hormones, anabolic effects on bone (manifested

as hyperstosis), atrophy/degeneration of testes, prostate and ovarian follicles and embryolethality and fetotoxicity (manifested as decreased fetal body weight). For RUXOLITINIB the predominant toxicities seen preclinically consisted of: myelosuppression, lymphoid depletion resulting in decreased erythropoiesis and lymphopoiesis, immunosuppression resulting in secondary infections in dogs, and embryo-lethality and fetotoxicity (manifested as decreased fetal body weight). For both compounds most of the findings were reversible or showed trends toward reversibility and can be readily monitored in the clinical setting. Preliminary clinical data available from ongoing trials in myelofibrosis with PANOBINOSTAT or RUXOLITINIB as single agents indicate thrombocytopenia as the principal overlapping dose-limiting toxicity. Fatigue, neutropenia and diarrhea are also listed as toxicities for PANOBINOSTAT. Although no combination PANOBINOSTAT and RUXOLITINIB toxicity studies have been conducted, based on clinical data with each, it appears likely that thrombocytopenia will be dose limiting when these agents are combined in the clinical setting.

In addition to identifying common target organ toxicities understanding the metabolism and elimination of each compound and how the presence of one compound might impact systemic drug concentrations of the other can further inform the potential for additive or synergistic toxicities. Based on in vitro metabolic profiling and results from clinical PANOBINOSTAT drug interaction studies, PANOBINOSTAT has shown to be a non-sensitive CYP3A substrate and a weak CYP2D6 inhibitor in patients. It has also been predicted to have minimal clinical risk with a non sensitive CYP3A substrate. RUXOLITINIB is also a non-sensitive CYP3A substrate and is not known to be a CYP inhibitor or inducer. Since CYP3A is the most abundant CYP enzyme, drugs with shared elimination pathway via CYP3A have not been shown to have compromised elimination. Therefore drug-interaction between PANOBINOSTAT and RUXOLITINIB is not expected by being CYP3A substrates. PANOBINOSTAT is a weak time-dependent CYP3A inhibitor and predicted to have no consequence on a non-sensitive CYP3A substrate, such as RUXOLITINIB. Since PANOBINOSTAT is also administered intermittently, its clinical impact on the chronic RUXOLITINIB administration is deemed even more remote. Based on available in vitro and clinical data, clinical drug interaction between PANOBINOSTAT and RUXOLITINIB is not expected. Based on preclinical data a summary of the integrative assessment for potential for additive and/or synergistic toxicity of combining PANOBINOSTAT with RUXOLITINIB is presented below.

Table 1-4 Integrative toxicological assessment of PANOBINOSTAT (LBH589) / RUXOLITINIB (INC424) combination

Target Organ	LBH589	INC424	Potential Impact of Combination
Genotoxicity	Positive in Ames and Chromosomal Aberration Assays	Not genotoxic	None predicted
Cardiovascular	QT prolongation (dog, human)	↓ in blood pressure, ↑ heart rate (dog), ↓ respiratory minute volume (rat) minimal heart fibrosis (rat)	None predicted ^a
Hematopoietic	Myelosuppression, lymphoid atrophy and/or depletion (↓ erythrocytes, granulocytes and platelets). Rat, dog) Thrombocytopenia, most common adverse event seen in patients	Myelosuppression, lymphoid atrophy, ↓ erythropoiesis and lymphopoiesis (rat, mouse, dog). Infections/infestations due to immunosuppression (dog) Thrombocytopenia, most common adverse event seen in patients, not observed in non clinical studies	Potential for additive or synergistic hematopoietic toxicity (thrombocytopenia most likely in patients)
Gastrointestinal	Degeneration/necrosis - epithelium of the small intestine, diarrhea (dog), atrophy of parotid gland (rat)	Inflammation and/or erosion of the small intestine (dog), Hyperplasia of non-glandular stomach (mouse)	Potential for additive gastrointestinal toxicity
Thyroid	Follicular epithelial hypertrophy, cytoplasmic vacuolation, reduced follicular colloid, variable changes in T3, T4 and TSH (rat, dog)	No change	None predicted
Reproductive	♂ Atrophy/degeneration of prostate and testes (oligospermia), ♀ atretic ovarian follicles and uterine atrophy (rat, dog). Embryo-lethal and fetotoxic, but not teratogenic (rat, rabbit)	Embryo-lethal and fetotoxic, but not teratogenic (rat, rabbit)	Embryo-fetal warning and highly effective birth control required clinically
Bone	Endosteal Hyperstosis (rat)	No change	None predicted

^a INC424 cardiovascular effects in dogs and rats were seen at maximal plasma concentrations (Cmax) and exposures (AUC) that were 10 -50-fold greater than those seen in patients at the MTD of 25 mg bid.

2 Rationale

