5.1 Patient population

Adult male or female patients ages 18 or older, who have been diagnosed with Primary myelofibrosis (PMF), Post-polycythemia vera related myelofibrosis (Post PV MF) or Post Essential Thrombocythemia related Myelofibrosis (Post ET MF) as defined by the World Health Organization (WHO 2008), will be included in this study. These patients will be seen at the Mount Sinai School of Medicine Myeloproliferative Disorders Program.

Patients must be classified by the International Working Group for Myelofibrosis Research and Treatment (IWG-MRT) (Passamonti, 2010) and be either Intermediate-2: 3-4 points; or High Risk: 5 or more points. Patients can have either chronic phase (MF-CP), or accelerated phase (MF-AP) disease.

Patients may have received prior therapy for MF, but must discontinue chemotherapy for 3 weeks (except for hydroxyurea which can be discontinued 24 hours before starting RUXOLITINIB), and targeted therapy for 2 weeks prior to screening. Anagrelide can be continued up until 24 hours of starting the RUXOLITINIB. An exception are patients currently on at least 10mg BID of RUXOLITINIB for greater than 3 months and who have not shown an optimal response (i.e. without 50% reduction in palpable splenomegaly or 50% reduction in symptom burden). With a reduction of RUXOLITINIB to 10mg BID these patients may enter onto the study without stopping RUXOLITINIB. This trial will allow

patients who were treated with either HDACi's or JAK2 inhibitors, as long as these agents were not discontinued due to clinically relevant toxicities per the investigator.

Patients enrolled in this study are not permitted to participate in additional parallel investigational drug or device studies.

The investigator or designee must ensure that only patients who meet all the following inclusion and none of the exclusion criteria are allowed to enter study treatment in this study. Written informed consent must be obtained prior to any screening procedures.

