4. Other concurrent severe and/or uncontrolled medical conditions (e.g., uncontrolled diabetes or active or uncontrolled infection) including abnormal laboratory values, that could cause unacceptable safety risks or compromise compliance with the protocol
5. Patients using medications that have a relative risk of prolonging the QT interval or inducing torsade de pointes if treatment cannot be discontinued or switched to a different medication prior to starting study drug
6. Concomitant use of strong CYP3A4 inhibitors
7. Patients who have received targeted agents within 2 weeks or within 5 half-lives of the agent and active metabolites (whichever is longer) and who have not recovered from side effects of those therapies.
8. Chemotherapy within 3 weeks prior to screening are excluded (other than hydroxyurea at stable doses and will be discontinued 24 hours prior to starting study drug).
9. Patients with an active bleeding tendency or are receiving any treatment with therapeutic doses of sodium warfarin (Coumadin[®]) or coumadin derivatives. Patients will be allowed to enter study on aspirin at doses of 81mg/d.
10. Patients who have undergone major surgery≤ 4 weeks prior to starting study drug or who have not recovered from side effects of such therapy
11. Women who are pregnant or breast-feeding or women of childbearing potential (WOCBP) not using an effective method of birth control. WOCBP are defined as sexually mature women who have not undergone a hysterectomy or who have not been naturally postmenopausal for at least 12 consecutive months (i.e., who has had menses any time in the preceding 12 consecutive months). Women of childbearing potential must have a negative serum pregnancy test within 24hrs of receiving the first dose of study medication.
12. Male patients whose sexual partners are WOCBP not using effective birth control
13. Patients with a prior malignancy within the last 5 years (except for basal or squamous cell carcinoma, or *in situ* cancer of the cervix)
14. Disease associated with secondary MF such as metastatic carcinoma, lymphoma, myelodysplasia, hairy cell leukemia, mast cell disease or acute leukemia (including M7 disease or acute panmyelosis with MF)

6 Treatment

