7.1.2.1 Eligibility screening

Patients must meet all inclusion and exclusion criteria at Screening in order to be eligible for the study. Patient eligibility will be confirmed by the investigative staff and captured within the source documents maintained at the site. Only when eligibility is confirmed will the patient be assigned to a dose level. The Primary Investigator/co-investigators must approve eligibility and will assign the patient to the appropriate dose level.

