8.4 Pregnancies

To ensure patient safety, each pregnancy in a patient on study treatment must be reported to the PPHS of MSSM and the FDA. The pregnancy should be followed up to determine outcome, including spontaneous or voluntary termination, details of the birth, and the presence or absence of any birth defects, congenital abnormalities, or maternal and/or newborn complications.

Instances of pregnancies and positive pregnancy tests should be collected for all patients who have conceived after receiving study medication. Pregnancies that are noted prior to administration of study medication but after signing informed consent may require reporting if they are considered to be associated to the conduct of the study by the investigator. Pregnancy data should be submitted to the Local Safety Helpdesk at the CPO via the clinical trial pregnancy form within 24 hours of the site becoming aware of the information. If the pregnancy has resulted in a Serious Adverse Event (SAE), a SAE form should be completed irrespective of whether or not the patient has received the study medication.

Pregnancy outcomes must be collected for the female partners of any males who took study treatment in this study. Consent to report information regarding these pregnancy outcomes should be obtained from the mother.

Since PANOBINOSTAT is associated with potential genotoxicity per the current labeling information (current Investigator's Brochure), as such this protocol includes highly effective contraception per the Novartis pregnancy prevention guidelines document. Where applicable and able the female pregnant partner of the male study participant may also be informed of this information as appropriate and feasible.

Principal Investigator Responsibilities for pregnancy reporting:

- Report all pregnancies for all female trial participants, including outcome, and adverse events during pregnancy.

- Report all pregnancies for pregnant partners of male clinical trial participants.
- Report all outcomes and any adverse events experienced by the pregnant partner during pregnancy
- Obtain follow-up for outcome and other data as requested by CTSO/CPO.
- Adhere to general SAE reporting timelines and guidelines.

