11.3 Informed consent procedures

Eligible patients may only be included in the study after providing written (witnessed, where required by law or regulation), IRB/IEC/REB-approved informed consent, or, if incapable of doing so, after such consent has been provided by a legally acceptable representative of the patient. In cases where the patient's representative gives consent, the patient should be informed about the study to the extent possible given his/her understanding. Informed consent must be obtained before conducting any study-specific procedures (i.e. all of the procedures described in the protocol). The process of obtaining informed consent should be documented in the patient source documents. The date when a subject's Informed Consent was actually obtained will be captured in their eCRFs.

Women of child bearing potential should be informed that taking the study medication may involve unknown risks to the fetus if pregnancy were to occur during the study and agree that in order to participate in the study they must adhere to the contraception requirement for the duration of the study. If there is any question that the patient will not reliably comply, they should not be entered in the study.

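### Exclusion criteria 11 and 12 ask only for effective birth control, while Table 1-4 and section 8.4 set the standard at highly effective

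*Combined protocol and SAP*

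**What the plan says.** Two places set the higher standard.

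- **Section 1.4.2, Table 1-4, Reproductive row.** Both drugs are recorded as embryo-lethal and fetotoxic in animals, and the consequence drawn for the combination is "Embryo-fetal warning and highly effective birth control required clinically". The Genotoxicity row of the same table records panobinostat as positive in two assays.
- **Section 8.4.** Because of panobinostat's potential genotoxicity, "as such this protocol includes highly effective contraception per the Novartis pregnancy prevention guidelines document".

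Two criteria in the exclusion list under section 5.2 set a lower one.

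- **Exclusion 11** covers "women of childbearing potential (WOCBP) not using an effective method of birth control".
- **Exclusion 12** covers "Male patients whose sexual partners are WOCBP not using effective birth control".

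These criteria decide entry. Section 5.1 states that "only patients who meet all the following inclusion and none of the exclusion criteria are allowed to enter study treatment", and section 7.1.2.1 repeats it: "Patients must meet all inclusion and exclusion criteria at Screening in order to be eligible for the study".

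Two other places touch on contraception without giving a level. Section 11.3 tells women of childbearing potential that "they must adhere to the contraception requirement for the duration of the study", and adds: "If there is any question that the patient will not reliably comply, they should not be entered in the study". Section 7.1.2.3 lists a discussion of prevention methods at screening.

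**The concern.** The protocol identifies a reproductive hazard, states the level of contraception it calls for, and then does not carry that level into the criteria that staff apply when admitting a patient. If *effective* is a looser term than *highly effective*, someone using a method in between passes screening although the protocol's own assessment says that method is not enough.

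What is at stake is exposure of an embryo or fetus to drugs that are embryo-lethal and fetotoxic in animals, one of them positive in genotoxicity assays. The exact wording also matters more here because external checks are few: section 9.1 provides no site monitoring and section 8.6 no data monitoring committee.

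**Working it through.** The plan gives no figure on this point, so the check compares the text and then asks how many patients could be affected.

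**Step 1. Where each level appears**

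| Place | Level stated | Decides entry? | Covers men? |
|---|---|---|---|
| Table 1-4, Reproductive row | highly effective | No | Not specified by sex |
| Section 8.4 | highly effective, by external guideline | Not stated as an entry condition | Not limited by sex |
| Exclusion 11 | effective | Yes | No |
| Exclusion 12 | effective | Yes | Yes |
| Section 11.3 | none given | Yes, where compliance is in doubt | No |
| Section 7.1.2.3 | none given | No | Not specified by sex |

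Two places say highly effective, two entry criteria say effective, and two places give no level. No cross-reference runs from section 5.2 to section 8.4. Neither term is defined, and no accepted methods are listed.

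**Step 2. Who is treated differently under the two wordings**

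| Contraception used | Under highly effective | Under exclusions 11 and 12 as written |
|---|---|---|
| Highly effective method | Eligible | Eligible |
| Effective but not highly effective method | Not eligible | **Eligible** |
| No effective method | Not eligible | Not eligible |

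Only the middle row changes.

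**Step 3. Size**

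Affected patients = N × p × q, where

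- N = 33 to 58 is the planned number of patients (Summary and section 10.8);
- p is the share who are women of childbearing potential or men with such a partner;
- q is the share of those whose method is effective but not highly effective.

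The documents give neither p nor q. If q = 0, the result is 58 × p × 0 = 0 for any p, so the lower bound is 0. No upper bound can be supported.

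**Step 4. Whether other provisions close the gap**

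- *Women.* Section 11.3 can bar a woman whose compliance is doubtful, but it names no level. Exclusion 11 and section 7.2.5.6 require a serum pregnancy test before dosing, and 7.2.5.6 adds a urine test on day 1 of each cycle. These tests detect a pregnancy; they do not prevent one.
- *Men.* Neither the 11.3 bar nor the testing applies to them. Exclusion 12 is their only contraception criterion for entry. Section 8.4 nevertheless requires partner pregnancies to be reported, so the protocol recognises the risk.

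**The case against.** The strongest reply is that section 8.4 is operative protocol text. It says the protocol includes highly effective contraception, names a standard, and is not limited by sex. On that reading the requirement in 11.3 is naturally the 8.4 standard, and exclusions 11 and 12 are merely loosely worded. This has some force: the higher standard is present in the protocol, and for women the criteria are not the only barrier. But 8.4 is the pregnancy-reporting section, nothing in 5.2 points to it, and 5.1 and 7.1.2.1 tie entry to the listed criteria. If 8.4 is meant to govern, the criteria need to say so.

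Other points on that side also deserve weight:

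- **Undefined terms.** Whether any real method falls between the two levels depends on a guideline that is not reproduced. The consent pages are not available either and may state the higher level. The mismatch in wording is certain; its practical effect is not.
- **Older population.** The protocol gives a median age at diagnosis of 65 for primary myelofibrosis, and medians of 68 and 66 in the two pivotal ruxolitinib trials. Women of childbearing potential are therefore likely to be few. Entry is open from age 18, however, and exclusion 12 depends on the partner's status, not the patient's age.
- **Toxicology in full.** Table 1-4 also records both drugs as not teratogenic in rat and rabbit, and predicts no combination effect on genotoxicity. That second entry concerns what is added by combining the drugs and does not cancel panobinostat's own positive assays. With these findings in view, the table still concludes that the higher level is needed.
- **Nature of the fault.** This is an inconsistency of wording rather than a deliberate design choice, and the text to correct is in 5.2, not in Table 1-4. That is right, and it does not change the remedy.

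**Conclusion.** The concern holds. Two exclusion criteria are looser than the safety requirement the protocol states in Table 1-4 and says in 8.4 that it includes. The gap is widest for men with partners of childbearing potential, who are not covered by 11.3 or by pregnancy testing.

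The conclusion about wording rests on the current text alone. The conclusion that a patient could be admitted below the required level assumes that *effective* and *highly effective* differ in practice and that staff apply the criteria as written. The number of such patients is unknown and may be 0. This is a participant-safety point that should be corrected; it has no bearing on endpoints, sample size, power or error rates.

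**What to change.** - In exclusions 11 and 12, replace effective with highly effective and cite the standard named in section 8.4. Listing the accepted methods there would let staff apply the criteria without the external guideline.
- In section 11.3, state the same level and extend the text to men with partners of childbearing potential.

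The cost is a wording amendment to two criteria and one consent paragraph, with possibly a few more screen failures. No analysis changes.
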